9.6 Biomarkers

Biomarker analysis will be performed on blood and tumor samples to evaluate predictive and pharmacodynamic markers for **CAR T cell therapy** and described in Section 10.1.

9.7 Description of Study Periods

9.7.1 Screening

The screening period begins on the date the subject signs the IRB/IEC approved ICF and continues through confirmation of enrollment. Informed consent must be obtained before completion of any non-standard of care study specific procedures. Procedures that are part of standard of care are not considered study specific procedures and may be performed prior to obtaining consent and used to confirm eligibility. Confirmation of this data must occur within the time allowance as outlined below and in the SOA.

After written informed consent has been obtained, subjects will be screened to confirm study eligibility and participation. Only subjects who meet the eligibility criteria listed in [Section 4](#) will be enrolled in the study. If at any time prior to enrollment the subject fails to meet the eligibility criteria, the subject should be designated as a screen failure on the subject screening log with the reasons for failing screening.

The following assessments/procedures are to be completed during the screening period at the time points outlined in the SOA:

- Medical history and disease assessment
- Physical examination
 - Subjects with symptoms of central nervous system malignancy such as new onset severe headaches, neck stiffness, or any focal neurologic findings on physical exam will have lumbar puncture for examination of cerebral spinal fluid.
- Vital signs, including blood pressure, heart rate, oxygen saturation, and temperature
- ECOG performance status

- Imaging Studies
 - PET CT post-CAR T cell therapy
 - PET-CT performed following the subject's therapy and prior to signing the consent may be used for confirmation of eligibility.
 - PET CT should be performed as close to enrollment as possible.
- Labs
 - Chemistry panel
 - CBC with differential
- Serious Adverse Event reporting (refer to [Section 8](#) for safety reporting guidelines)
- Concomitant medications documentation and previous cancer treatment history
- Once eligibility confirmed, collection of archived tumor sample, as well as fresh tumor sample(s) after RT.

9.7.2 Enrollment Period & RT simulation/planning

No specific restrictions are made for the use of RT after biopsy-confirmed relapse following CAR T cell therapy. Prior RT is not an exclusion criterion given the technologies available to safely deliver re-irradiation in many scenarios with modern technology. The RT simulation consists of imaging patients in the treatment position with using custom immobilization. After a planning period of 7-14 days, depending on complexity of treatment plan, patients begin radiation therapy. PET-CT imaging will be repeated if >28 days from prior imaging and enrollment.

9.7.3 RT Treatment

Patients are seen weekly during RT as per standard of care to monitor toxicities of RT. Subject will allow study personnel to continue to access medical records so that information related to subjects health condition and initial treatment response may be obtained. The following procedures will be completed for subjects as outlined in the SOA:

- Physical exam
- Vital signs, including blood pressure, heart rate, oxygen saturation, and temperature
- Labs
 - Chemistry Panel
 - CBC with differential
 - Cytokine levels
 - Lymphocyte subsets
 - Translational lab collection.
- Adverse/Serious Adverse Event reporting (refer to [Section 8](#) for safety reporting guidelines)
- Concomitant medications documentation

If a subject is admitted to the hospital with any **RT, CAR T-** related adverse event(s), the following labs will be collected **on the day of hospital re-admission and then weekly through and including on the day of discharge**:

- Translational labs (two 10cc purple top tubes)
- Cytokines (one 10cc red top tube)

9.7.4 Post RT Period

Patients are seen weekly for one month following RT. Subject will allow study personnel to continue to access medical records so that information related to subjects health condition and initial treatment response may be obtained. The following procedures will be completed for subjects as outlined in the SOA:

Seven to fourteen days after beginning RT, patients will undergo a core-needle biopsy (FNA acceptable if core-needle unable to be done for any reason). This biopsy will allow a direct comparison of inflammatory cytokine and T cell infiltration into the tumor in comparison to pre-RT biopsy that confirmed refractory disease. If it is deemed unsafe to proceed biopsy may be deferred as other immune correlates will be collected from peripheral blood and serum.

- Physical exam
- Vital signs, including blood pressure, heart rate, oxygen saturation, and temperature
- Labs
 - Chemistry Panel
 - CBC with differential
 - Cytokine levels
 - Lymphocyte subsets
 - Translational lab collection.
- Adverse/Serious Adverse Event reporting (refer to [Section 8](#) for safety reporting guidelines)
- Concomitant medications documentation

If a subject is admitted to the hospital with any **RT, CAR T-** related adverse event(s), the following labs will be collected **on the day of hospital re-admission and then weekly through and including on the day of discharge**:

- Translational labs (two 10cc purple top tubes)
- Cytokines (one 10cc red top tube)

At any time during the post treatment assessment period, if a subject progresses and is either not eligible for re-treatment or chooses not to pursue re-treatment, the subject will proceed directly to the Month 3 visit and be followed for survival, subsequent therapy and disease outcomes in the long term follow-up period. A translational lab set **and serum sample (for cytokine evaluation)** should be collected at the time of progression, prior to starting any subsequent anti-cancer therapy.

9.7.5 Long-term Follow-up Period

All subjects who complete the study, and those who withdraw from the study after receiving RT for reasons other than death, will be asked to participate in the long-term follow-up portion of this study up to 12 months from CAR-T infusion, with a focus on long-term efficacy and safety. These patients will also have long-term follow-up as part of the FDA mandated CIBMTR CAR T cell therapy registry.

The following procedures will be completed for subjects who are enrolled at the time points of 6, 9, and 12 months following CAR-T infusion, as outlined in the SOA (Long-term Follow-up Period) Table 3:

- Physical exam
- CTCAE/PRO-CTCAE Surveys
- PET-CT/ Disease assessment at 6 and 12 months per standard of care
- Survival status
- Labs
 - CBC with differential
 - Cytokine levels
 - Lymphocyte subsets
 - Translational lab collection.
- Subsequent therapy for the treatment of NHL
- **Refer to Sections 8.4** for targeted adverse/serious adverse event reporting
 - Including neurological, hematological, infections, autoimmune disorders, and secondary malignancies
- Targeted concomitant medication documentation (for 12 months or until disease progression, whichever occurs first)
 - Including gammaglobulins, immunosuppressive drugs, anti-infectives, and vaccinations

Subjects may be contacted by telephone to confirm survival status and report targeted concomitant medication use.

If a subject progress in the LTFU phase, the subject will continue to be followed for survival status and subsequent therapy for the treatment of NHL. A translational lab sample and **serum (for cytokine evaluation)** should be collected at the time of progression as part of CAR T cell therapy protocol, prior to starting any subsequent anti-cancer therapy.

Should the subject fail to return to the clinic for a scheduled protocol specific visit, sites will need to make 2 attempts by a combination of telephone and mail to contact the subject. Sites must document both attempts to contact the subject. If a subject does not respond within 1 month after the second contact the subject will be considered lost to follow-up and no additional contact will be required.

As patients will be receiving commercial product, patients will also have long-term follow-up as part of FDA mandated CAR T cell therapy registry.

Table 2. Schedule of Assessments

Procedures	Screening	Enrollment & RT Planning	Radiotherapy		Post Radiotherapy Period			
			Day 0	Weekly through completion (± 7 days)	Week 1 Post-Treatment (± 7 days)	Week 2 Post-Treatment (± 7 days)	Week 3 Post-Treatment (± 7 days)	Week 4 Post-Treatment (± 7 days)
Day	No longer than 14 days from biopsy and within 28 days of enrollment	Within 14 days of Initiation of Radiotherapy	Day 0	Weekly through completion (± 7 days)	Week 1 Post-Treatment (± 7 days)	Week 2 Post-Treatment (± 7 days)	Week 3 Post-Treatment (± 7 days)	Week 4 Post-Treatment (± 7 days)
Informed consent	X							
Medical history	X							
ECOG Performance Status	X		X	X	X			
CRS/ICANS Consensus Grading	X		X	X				
CTCAE/PRO-CTCAE Surveys		X			X			
Tumor Biopsy	X ^{1,2} (w/in 90 days of CAR T infusion)				X ²			
PET-CT/ disease assessment	X ³							
RT Planning		X						
Physical exam	X			X				
Vital signs (BP, HR, O ₂ sat, temp)	X			X				
Weight (plus Height at screening)	X							
Blood draw for Chemistry panel	X		X	X	X	X	X	X
Blood draw for CBC w/differential	X		X	X	X	X	X	X
Blood draw for C-reactive protein (CRP)	X		X	X	X	X	X	X
Blood draw for Lymphocyte subsets ³			X	X	X	X	X	X
Blood draw for Cytokines ^{4,5}			X	X	X	X	X	X
Blood draw for translational lab collection ^{4,6}			X	X	X	X	X	X
Radiotherapy ⁷			X					
Adverse events/ Concomitant medication	X	X	X	X	X	X	X	X

¹ Tumor biopsy: Either FFPE tumor block or up to 20 unstained slides. Fresh tumor biopsies are preferred however archival tissue is acceptable if obtained prior to screening period but following CAR-T infusion without intervening therapy.

² Tumor biopsy may be deferred if not deemed clinically appropriate and safe.

³ PET-CT (Neck-Chest-Abdomen-Pelvis)/disease assessment: If recent PET-CT performed > 45 days from enrollment, baseline scans must be repeated.

⁴ Prior to radiotherapy on Day 0, then weekly through 4 weeks post radiotherapy.

⁵ Cytokines: 5cc red top tubes

⁶ Translational Labs: Two 10cc purple top tubes

⁷ Radiotherapy: Individual patient course may vary depending on optimal treatment strategy.

⁸ Tumor biopsy: Either FFPE tumor block or up to 20 unstained slides. If possible, repeat tumor biopsy to be obtained in the event of disease progression.

Table 3. Schedule of Assessments (Long-term Follow-up Period)

Procedure	Long Term Follow-up Period (Each visit calculated from CAR-T infusion)		
	Month 6	Month 9	Month 12
Physical exam	X	X	X
CTCAE/PRO-CTCAE Surveys	X	X	X
PET-CT/disease assessment ¹	X		X
Survival Status	X	X	X
Blood draw for CBC w/differential ³	X	X	X
Blood draw for Lymphocyte subsets ³	X	X	X
Blood draw for Cytokines ^{4,5}	X	X	X
Blood draw for translational lab collection ^{4,6}	X	X	X
Targeted AEs/SAEs ⁷	X	X	X
Targeted concomitant medication ⁸	X	X	X
Subsequent therapy for NHL ⁹	X	X	X

¹ PET-CTs/disease assessments will continue through Month 12 or until disease progression, whichever comes first, as is performed per standard of care.

³ Subjects will continue to provide samples for CBC w/diffs, lymphocyte subsets and anti-CD19 CAR T cells through Month 12 as per standard of care

⁴ Monthly starting 6 months from CAR-T infusion

⁵ Cytokines: 5cc red top tubes

⁶ Translational Labs: Two 10cc purple top tubes

⁷ Targeted AEs/SAEs will be collected for 24 months or until disease progression (whichever occurs first)

⁸ Targeted concomitant medications will be collected for 24 months or until disease progression (whichever occurs first)

⁹ Subsequent therapy administered after CAR-T infusion for a subjects' disease such as non-study specified chemotherapy, immunotherapy, targeted agents, as well as stem cell transplant must be collected until subject completes the long term follow up period, is considered lost to follow up, withdraws consent, or dies. Subjects may be contacted by telephone to collect information about subsequent therapy for NHL and to assess survival status.

10. MEASUREMENT OF EFFECT

10.1 Disease Response Assessment

Subjects will be evaluated for disease response by the site investigator at times indicated in the SOA. Disease assessments will be evaluated per the Lugano Criteria¹ for Malignant Lymphoma²³ as applicable (appendix B). Flow cytometric, molecular or cytogenetic studies will not be used to determine response.

Pre-RT PET-CT scans of the neck, chest, abdomen and pelvis is required. **Subjects will undergo additional PET-CT tumor assessment as part of standard of care.**

After RT, disease assessments will be used to determine the time when progressive disease occurs. Subjects with symptoms suggestive of disease progression should be evaluated for progression at the time symptoms occur even if it is off schedule as per the SOA.

11. DATA REPORTING / REGULATORY REQUIREMENTS

Adverse event lists, guidelines, and instructions for AE reporting can be found in Section 8.0 (Adverse Events: List and Reporting Requirements).

11.1 Data Reporting

11.1.1 Method

The Office of Data Quality (ODQ) will collect, manage, and perform quality checks on the data for this study.

11.1.2 Responsibility for Data Submission

Investigative sites within DF/HCC or DF/PCC are responsible for submitting data and/or data forms to the Office of Data Quality (ODQ) in accordance with DF/HCC policies.

11.2 Data Safety Monitoring

The DF/HCC Data and Safety Monitoring Committee (DSMC) will review and monitor toxicity and accrual data from this study. The committee is composed of medical oncologists, research nurses, pharmacists and biostatisticians with direct experience in cancer clinical research. Information that raises any questions about participant safety will be addressed with the Overall PI and study team. In addition to the DF/HCC DSMC, a safety review team (SRT) comprised of the study sponsor and Kite/Gilead, will review the safety data and make recommendations on further study conduct as described below.

The DSMC will review each protocol up to four times a year with the frequency determined by

the outcome of previous reviews. Information to be provided to the committee may include: up-to-date participant accrual; current dose level information; DLT information; all grade 2 or higher unexpected adverse events that have been reported; summary of all deaths occurring within 30 days of intervention for Phase I or II protocols; for gene therapy protocols, summary of all deaths while being treated and during active follow-up; any response information; audit results, and a summary provided by the study team. Other information (e.g. scans, laboratory values) will be provided upon request.

12. STATISTICAL CONSIDERATIONS

The primary objective is to ascertain the safety and toxicity of radiotherapy in patients with hematologic malignancies who will undergo CD19-targeted CAR T cell therapy. The secondary objectives are to evaluate the efficacy of radiotherapy in these patients. Exploratory objectives include assessing T cell infiltration, including CAR T cells, into lymphoma following radiotherapy and evaluating mechanisms of interplay between radiotherapy and CAR T cell therapy, by examining serum cytokine levels and expression changes of key pathway mediators in lymphoma biopsy samples before and after radiotherapy

This protocol is designed to **assess the impact of radiation therapy.**

12.1 Study Endpoints

Primary Endpoint:

- Rate and severity of RT-related toxicity as per CTCAE v5.0 criteria during RT or within the first 30 days of completing RT.

Secondary Endpoints:

- **Duration of response (DOR):** Among subjects who experience an objective response, DOR is defined as the date of their first objective response (which is subsequently confirmed) to disease progression per Lugano criteria¹ or death regardless of cause. Subjects not meeting the criteria for progression or death by the analysis data cutoff date will be censored at their last evaluable disease assessment date and their response will be noted as ongoing.
- **Objective response rate (ORR) per IRRC:** ORR per IRRC is defined as the incidence of either a complete response or a partial response by Lugano criteria¹ as determined by the IRRC. All subjects that do not meet the criteria for an objective response by the analysis data cutoff date will be considered non-responders.
- **Progression-free Survival (PFS):** PFS is defined as the time from RT completion date to the date of disease progression per Lugano criteria¹ or death from any cause. Subjects not meeting the criteria for progression by the analysis data cutoff date will be censored at their last evaluable disease assessment date.

- **Overall survival (OS):** OS is defined as the time from RT completion to the date of death. Subjects who have not died by the analysis data cutoff date will be censored at their last contact date.

Exploratory Endpoints:

- Levels of anti-CD19 CAR T cells in blood
- Levels of cytokines in serum
- Incidence of anti-axicabtagene ciloleucel antibodies
- Investigation of potential biomarker development based on assessment of blood cells, tumor cells and the proposed actions of the investigational product.

External collaboration with BostonGene, a biotechnology company: anonymized tumor samples from core-needle biopsy and blood (paired pre-RT and post-RT samples for each patient) will be made available for Next-Generation Sequencing (NGS) and analysis following sample collection from all enrolled patients. BostonGene will perform NGS and analysis. In order to assist with clinical correlation of NGS data, BostonGene will be provided with anonymized data for each sample with regard to clinical characteristics (age, diagnosis, prior therapies, response on imaging, pathology results, blood counts, and cytokine profiles). Anonymized patient samples will be delivered by secure courier. All data will be anonymized (free from any patient identifiers) and securely transmitted with approved methods as per MGH IS.

The primary objective of this study is to assess safety and toxicity of RT following CAR T cell therapy. The assessment of ORR is a secondary objective, and the analysis will be descriptive.

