12.4 Analysis of Primary and Secondary Endpoints

Planned Method of Analysis

The primary analysis of all treated subjects will take place once they have had the opportunity to be followed for 6 months.

Descriptive analyses may occur at any time.

Objective Response Rate

The incidence of objective response and exact 2-sided 95% confidence intervals will be generated.

Duration of Response

The competing-risk analysis method ^{24,25} will be used to estimate the cumulative incidence of relapse. The cumulative incidence of relapse in the presence of non-disease related mortality (the competing risk) will be estimated along with 2-sided 95% confidence intervals at 3-month intervals.

Progression-free Survival

Kaplan-Meier estimates and 2-sided 95% confidence intervals will be generated for progression-free survival time. Estimates of the proportion of subjects alive and progression-free at 3-month intervals will be provided.

Overall Survival

Kaplan-Meier estimates and 2-sided 95% confidence intervals will be generated for OS. Estimates of the proportion of subjects alive at 3-month intervals will be provided.

Safety

Subject incidence rates of adverse events including all, serious, fatal, CTCAE version 5.0 Grade 3 or higher and treatment related AEs reported throughout the conduct of the study will be tabulated by preferred term and system organ class. Changes in laboratory values and vital signs will be summarized with descriptive statistics. The incidence of concomitant medications will be summarized.

Tables and/or narratives of deaths through the long-term follow-up and treatment related SAEs will be provided.

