12.5 Reporting and Exclusions

The statistical reporting of the safety and efficacy endpoints will be compared to historical controls of patients with refractory disease following CAR T cell therapy who did not undergo RT. Subject incidence rates of axicel or tisacel-related adverse events, and ORRs will be summarized. DOR, PFS, and OS will also be summarized.

Analysis Subsets

Access to Individual Subject Treatment Assignments

This is a single arm, open-label study and subjects and investigators will be aware of treatment received. Data handling procedures for the the study will be devised to reduce potential sources of bias and maintain the validity and credibility of the study. These procedures will be outlined in the study statistical analysis plan and Trial Integrity Document.

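### DOR is defined to include any death, but the only analysis named for it counts relapse; PFS and OS start at RT completion, with no rule for a failure during RT or an unfinished course

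*Combined protocol and SAP*

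**What the plan says.** **Duration of response.** Section 12.1 says "DOR is defined as the date of their first objective response (which is subsequently confirmed) to disease progression per Lugano criteria", and continues "or death regardless of cause. Subjects not meeting the criteria for progression or death by the analysis data cutoff date will be censored". Progression and any death are therefore both events, and only subjects with neither are censored. Under the Duration of Response heading, section 12.4 names one method, a competing-risk analysis: "The cumulative incidence of relapse in the presence of non-disease related mortality (the competing risk) will be estimated". Section 12.5 adds "DOR, PFS, and OS will also be summarized" and names no estimator.

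**PFS and OS.** Section 12.1 says "PFS is defined as the time from RT completion date to the date of disease progression per Lugano criteria" (or death from any cause) and "OS is defined as the time from RT completion to the date of death". Section 12.4 applies Kaplan-Meier to both. On who is analysed, 12.4 says "The primary analysis of all treated subjects will take place once they have had the opportunity to be followed for 6 months", and no narrower efficacy population is stated.

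**Comparison.** Section 12.5 plans to set the safety and efficacy results against historical controls who had refractory disease after CAR T and no RT. No index date is given for them.

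**The concern.** A responder who dies without relapse has a DOR event under 12.1 and a competing event under 12.4. The one DOR analysis with a named method would therefore answer a different question from the one the endpoint asks.

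For PFS and OS the clock starts at the end of treatment, while the stated population is everyone treated. A subject who fails before that point, or never reaches it, has no usable time, and no rule says what to do. The choice would then be made after the data are seen, and it would concern the earliest failures.

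No decision threshold rests on these endpoints, and 12.2 bases the sample size of the larger study on safety and toxicity events. Section 2.1 does, however, make the case for RT depend on its being both safe and effective.

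**Working it through.** The plan gives no numerical figure for DOR, PFS or OS to reproduce. The sample size of 19 in 12.2 does not enter this point.

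**1. DOR: endpoint against estimator.** Let F_R(t) be the cumulative incidence of relapse and F_D(t) that of death without relapse. The endpoint in 12.1 is

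S(t) = 1 − F_R(t) − F_D(t).

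The method in 12.4 gives F_R(t). Its complement exceeds S(t) by exactly F_D(t), so the two agree only if no responder dies without relapse. In addition, 12.4 makes only death unrelated to disease the competing risk. A death from disease with no documented relapse is then neither the event nor the competing event.

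*Illustration by counts (assumed: 10 responders, complete follow-up, 3 relapses, 1 or 2 deaths without relapse; exact Clopper-Pearson intervals).*
- Cumulative incidence of relapse: 3/10 = 30% (7% to 65%).
- DOR events as defined: 4/10 = 40% (12% to 74%) or 5/10 = 50% (19% to 81%).

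*Illustration by rates (assumed constant hazards: relapse 0.08 per month, death without relapse d per month).* S(t) = exp(−(0.08 + d)t), F_R(t) = 0.08/(0.08 + d) × (1 − S(t)), gap = 1 − F_R(t) − S(t). Gaps are taken from unrounded values.

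| d | Month | DOR as defined | 1 − F_R | Gap (points) |
|---|---|---|---|---|
| 0.01 | 3 | 76.3% | 79.0% | 2.6 |
| 0.02 | 3 | 74.1% | 79.3% | 5.2 |
| 0.04 | 3 | 69.8% | 79.8% | 10.1 |
| 0.01 | 6 | 58.3% | 62.9% | 4.6 |
| 0.02 | 6 | 54.9% | 63.9% | 9.0 |
| 0.04 | 6 | 48.7% | 65.8% | 17.1 |

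**2. PFS and OS: which subjects lack a valid time.**

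| Case | Time from RT completion |
|---|---|
| Progression found from symptoms during RT, course then completed | PFS negative; OS valid |
| Death during RT | Negative against the planned end; strictly, no completion date exists |
| Course stopped early, subject alive | No time zero for PFS or OS |
| Silent progression during RT, first seen on a scan after RT | Positive, valid |
| Any failure after completion | Positive, valid |

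The fourth row limits the problem. Table 2 schedules no PET-CT between screening and the end of its post-RT weeks, and Table 3 places scans at months 6 and 12 after CAR T infusion. Section 10.1 asks for off-schedule evaluation when symptoms suggest progression. The affected subjects are therefore deaths during RT, symptom-detected progression during RT, and unfinished courses. Their number cannot be derived: the documents fix no course length and give no failure rate for this setting.

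*What one subject is worth (assumed: 8 of 20 event-free at 6 months).* All counted: 8/20 = 40% (exact interval 19% to 64%). One left out: 8/19 = 42.1%. Two left out: 8/18 = 44.4%.

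**3. Historical controls.** They had no RT, so they have no RT completion date. If their clock starts at an earlier milestone, the time up to RT completion is guaranteed survival for RT subjects counted from completion, but is at risk for controls. With no RT effect, the resulting difference is zero at a constant hazard, favours RT if failures come early, and goes against RT if the hazard rises. No size is given here, because it depends on a control start date that the documents do not supply.

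**The case against.** The strongest reply is that little turns on this. The endpoints are secondary, enrolment is about 20, and the interval around 8/20 spans 19% to 64%, wider than any shift shown above. Early deaths would not vanish either: 7.4.2 requires reporting of deaths within 3 months of RT, 12.4 tabulates fatal events and reports deaths, and the primary endpoint already covers toxicity during RT. Measuring from RT completion is a legitimate choice, and a one-line rule for earlier failures could also close the gap. Section 6.6.1 lets subjects decline study-required treatment and stay on study, but 6.1 calls RT standard of care, so 6.6.1 may not govern unfinished courses. DOR follow-up will be short at the primary analysis, and Kaplan-Meier does not cure that.

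All of this stands as a limit on size. None of it makes the method in 12.4 estimate the endpoint in 12.1, or supplies the missing rule.

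Two stronger readings are tempting and unsupported. A reader might infer that several of the 20 subjects would drop out of PFS and inflate it. No passage directs any exclusion, and silent progression during RT would be dated by a later scan. A reader might also infer that the historical comparison favours RT by a known amount. No control start date is given, the direction can go either way, and 12.5 defers bias-reducing data-handling procedures to a statistical analysis plan and Trial Integrity Document that are not among the documents reviewed.

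**Conclusion.** Two defects hold on the text. First, the analysis named for DOR does not estimate DOR as defined whenever a responder dies without relapse, and it leaves disease-related death without documented relapse unassigned. Second, PFS and OS have no valid time for a death or symptom-detected progression during RT (the latter for PFS only), or for a course that is never completed, although all treated subjects are to be analysed.

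The likely effect is small. The DOR gap equals the incidence of death without relapse, and the figures shown rest wholly on assumed counts and hazards. The number of subjects affected by the time origin is probably low and cannot be calculated from the documents. The missing index date for the historical controls is a secondary note, since a document not available here might address it. Both defects merit correction before analysis because the correction is cheap, not because a conclusion of the pilot depends on them.

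**What to change.** - **12.4, DOR.** Estimate time from first response to progression or any death by Kaplan-Meier, with 95% intervals at the 3-month points already planned. Keep the cumulative incidence of relapse as a separately named supplement, and say how a disease-related death without documented relapse is classified in it.
- **12.1, PFS and OS.** Start both at the date of first RT for all treated subjects, with RT completion as an optional sensitivity analysis. This matches section 9, which counts visits from the start of RT. Write the date of first RT and not Day 0: Table 2 uses Day 0 for the start of RT, but the glossary defines Study Day 0 as the first day of axicabtagene ciloleucel.
- **12.5.** Name an index date that RT subjects and controls both have, or report PFS, OS and DOR descriptively without that comparison.

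The first two changes are wording only, because the schedule already rests on the RT start date and follow-up already covers progression and survival. Estimates may move slightly in either direction with the new origin. A comparison on a common index date costs more: it needs dated control data, and no control source is described. Dropping the comparison for these endpoints avoids that cost.
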